# Appendix 15 WHO Toxicity Grading Scale for Determining the Severity of Adverse Events

ITEM	Grade 1 Toxicity	Grade 2 Toxicity	Grade 3 Toxicity	Grade 4 Toxicity
HEMATOLOGY	HEMATOLOGY			
Hemoglobin	9.5–10.5 g/dL	8.0-9.4 g/dL	6.5-7.9 g/dL	< 6.5 g/dL
Absolute Neutrophil Count	1000–1500/mm 	750–999/mm 	500–749/mm 	< 500/mm 
Platelets	75,000–99,000/mm 	50,000-74,999/mm 	20,000–49,000/mm 	<20,000/mm 
Prothrombin Time (PT)	1.01-1.25×ULN	1.26-1.5×ULN	1.51–3.0×ULN	>3×ULN
Activated Partial Thromboplastin (aPTT)	1.01–1.66 × ULN	1.67-2.33×ULN	2.34–3×ULN	>3×ULN
Fibrinogen	0.75-0.99×LLN	0.50-0.74×LLN	0.25-0.49×LLN	< 0.25 × LLN
Fibrin Split Product	20–40 μg/mL	41–50 μg/mL	51–60 μg/mL	>60 μg/mL
Methemoglobin	5%-9.9%	10.0%-14.9%	15.0%–19.9%	>20%
LIVER ENZYMES				
AST (SGOT)	1.25–2.5×ULN	2.6-5×ULN	5.1–10×ULN	> 10 × ULN
ALT (SGPT)	1.25–2.5×ULN	2.6-5×ULN	5.1–10×ULN	> 10 × ULN
GGT	1.25–2.5×ULN	1.6-5×ULN	5.1–10×ULN	>10×ULN
Alkaline Phosphatase	1.25-2.5×ULN	1.6–5×ULN	5.1–10×ULN	>10×ULN
Amylase	1.1–1.5×ULN	1.6-2.0 × ULN	2.1–5.0×ULN	>5.1×ULN
CHEMISTRIES				
Hyponatremia	130-135 mEq/L	123-129 mEq/L	116-122 mEq/L	<116 or mental status changes or seizures
Hypernatremia	146–150 mEq/L	151–157 mEq/L	158–165 mEq/L	> 165 mEq/L or mental status changes or seizures
Hypokalemia	3.0-3.4 mEq/L	2.5–2.9 mEq/L	2.0–2.4 mEq/L or intensive replacement Rx required or hospitalization required	<2.0 mEq/L or paresis or ileus or life-threatening arrhythmia
Hyperkalemia	5.6–6.0 mEq/L	6.1–6.5 mEq/L	6.6-7.0 mEq/L	>7.0 mEq/L or life-threatening arrhythmia
Hypoglycemia	55–64 mg/dL	40–54 mg/dL	30–39 mg/dL	<30 mg/dL or mental status changes or coma

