# 4.5.8 Laboratory, Biomarker, and Other Biological Samples

At scheduled visits, specimens should be collected prior to study eye treatment. Fasting is not required prior to specimen collection. The specimens will be forwarded to the central laboratory. The central laboratory will either perform the analysis or forward samples to Sponsor or its designee for analysis and/or storage. Instructions for obtaining, processing, storing, and shipping of all specimens are provided in the laboratory manual. Laboratory supply kits will be provided to the sites by the central laboratory. See Appendix 1 and Appendix 2 for sample collection timepoints.

Samples will be collected for the following analyses:

- Hematology: WBC count, RBC count, hemoglobin, hematocrit, platelet count, and differential count (neutrophils, eosinophils, basophils, monocytes, lymphocytes, and other cells)
- Chemistry panel (serum): sodium, potassium, glucose, BUN or urea, creatinine, total protein, albumin, total and direct bilirubin, ALP, ALT, and AST
- Coagulation: INR, aPTT, and PT
- Lipids: cholesterol, LDL cholesterol, HDL cholesterol, and triglycerides
- Pregnancy test

All women of childbearing potential will have a serum pregnancy test at screening. Urine pregnancy tests will be performed at specified subsequent visits. If a urine pregnancy test is positive, it must be confirmed by a serum pregnancy test.

- Serum samples for measurement of anti-FHTR2163 antibodies (ADAs)
- Serum samples to measure FHTR2163 concentration
- Aqueous humor samples to measure FHTR2163 concentration
- Aqueous humor samples for determination of biomarkers related to HtrA1 activity and disease progression
- Plasma samples for exploratory research on biomarkers related to HtrA1 and GA
- Screening whole blood sample for polymerase chain reaction genotyping of HtrA1 risk-variant carrier status (rs10490924)
- Whole blood clinical genotyping sample for genomic research aimed at exploring inherited genome variations associated with AMD and the response to study drug. Analysis may include targeted single-nucleotide polymorphism genotyping or sequencing for rare variants. At participating sites, this sample may also be used for NGS methods that may include WGS or WES (see Section 4.5.9).

For sampling procedures, storage conditions, and shipment instructions, see the laboratory manual.

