# 5.3.3 Assessment of Severity of Adverse Events

The WHO toxicity grading scale (see Appendix 15) will be used for assessing adverse event severity. Table 2 will be used for assessing severity for adverse events that are not specifically listed in the WHO toxicity grading scale.

For adverse events of IOI, severity assessment ideally should be aligned with the grading scale for assessment of anterior chamber flare or cells and vitreous chamber (see Appendix 6).

Table 2 Adverse Event Severity Grading Scale for Events Not Specifically Listed in WHO Toxicity Grading Scale

Grade	Severity
1	Mild; transient or mild discomfort (<48 hours); no medical intervention or therapy required
2	Moderate; mild to moderate limitation in activity; some assistance may be needed; no or minimal medical intervention or therapy required
3	Severe; marked limitation in activity; some assistance usually required; medical intervention or therapy required; hospitalization possible
4	Life-threatening; extreme limitation in activity; significant assistance required; significant medical intervention or therapy required, hospitalization or hospice care probable

Notes: Developed by the Division of Microbiology and Infectious Diseases.

Regardless of severity, some events may also meet seriousness criteria. Refer to definition of a serious adverse event (see Section 5.2.2).

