# 5.3.5.7 Abnormal Laboratory Values

Not every laboratory abnormality qualifies as an adverse event. A laboratory test result must be reported as an adverse event if it meets any of the following criteria:

- Is accompanied by clinical symptoms
- Results in a change in study treatment (e.g., dosage modification, treatment interruption, or treatment discontinuation)
- Results in a medical intervention (e.g., potassium supplementation for hypokalemia) or a change in concomitant therapy
- Is clinically significant in the investigator's judgment

It is the investigator's responsibility to review all laboratory findings. Medical and scientific judgment should be exercised in deciding whether an isolated laboratory abnormality should be classified as an adverse event.

If a clinically significant laboratory abnormality is a sign of a disease or syndrome (e.g., ALP and bilirubin  $5 \times$  upper limit of normal (ULN) associated with cholestasis), only the diagnosis (i.e., cholestasis) should be recorded on the Adverse Event eCRF.

If a clinically significant laboratory abnormality is not a sign of a disease or syndrome, the abnormality itself should be recorded on the Adverse Event eCRF, along with a descriptor indicating whether the test result is above or below the normal range (e.g., "elevated potassium," as opposed to "abnormal potassium"). If the laboratory abnormality can be characterized by a precise clinical term per standard definitions, the clinical term should be recorded as the adverse event. For example, an elevated serum potassium level of 7.0 mEq/L should be recorded as "hyperkalemia."

Observations of the same clinically significant laboratory abnormality from visit to visit should only be recorded once on the Adverse Event eCRF (see Section 5.3.5.6 for details on recording persistent adverse events).

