#### 6.5 SAFETY ANALYSES

The safety analysis population will consist of all randomized patients who received at least one FHTR2163 injection or sham control, with patients grouped according to treatment received. Safety summaries will be presented for all treated patients.

Safety will be assessed through descriptive summaries of adverse events, ocular assessments (e.g., inflammation, IOP, BCVA), clinical laboratory evaluation, ocular imaging, and immunogenicity against FHTR2163.

Verbatim descriptions of adverse events will be summarized by mapped term, appropriate thesaurus level, and toxicity grade (if applicable) (see Section 5.3.3).

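### Appendix 15 puts alkaline phosphatase values from 1.6 to 2.5 × ULN in both Grade 1 and Grade 2, and no rule in the protocol says which grade to record

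*Combined protocol and SAP*

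**What the plan says.** Section 5.3.3 makes Appendix 15 the operative rule: "The WHO toxicity grading scale (see Appendix 15) will be used for assessing adverse event severity". The fallback is limited to other events: "Table 2 will be used for assessing severity for adverse events that are not specifically listed in the WHO toxicity grading scale".

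In Appendix 15, under liver enzymes, the row "Alkaline Phosphatase" gives 1.25–2.5 × ULN for Grade 1, 1.6–5 for Grade 2, 5.1–10 for Grade 3 and above 10 for Grade 4. The GGT row has the same four bands.

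Alkaline phosphatase (ALP) is measured in this trial. The serum chemistry list in Section 4.5.8 ends with "total and direct bilirubin, ALP, ALT, and AST". GGT does not appear in that list.

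The grade is used later. Section 2.2 names the severity of ocular and systemic adverse events among the safety endpoints, and Section 6.5 summarizes adverse events by toxicity grade where one applies. Section 5.3.5.7 limits which laboratory values reach that stage: "Not every laboratory abnormality qualifies as an adverse event".

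**The concern.** A severity scale should give one grade for one value. For ALP it gives two over a continuous range, and that range is most of what the table calls Grade 1. Two investigators who both follow the protocol could record an ALP of 2.0 × ULN as Grade 1 and as Grade 2.

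The same ambiguity reaches the recording of change. Section 5.3.5.6 asks for increases in the severity of a persistent event to be captured. Whether a rise from 1.4 to 1.8 × ULN is such an increase cannot be decided from the table, because 1.8 can be read as either grade.

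What is at stake is the consistency of the grade column in the adverse event tables for this one analyte.

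**Working it through.** **Inputs.** All bounds come from Appendix 15, in multiples of ULN.

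| Row | Grade 1 | Grade 2 | Grade 3 | Grade 4 |
|---|---|---|---|---|
| ALP | 1.25–2.5 | 1.6–5 | 5.1–10 | >10 |
| GGT | 1.25–2.5 | 1.6–5 | 5.1–10 | >10 |
| AST, ALT, BUN | 1.25–2.5 | 2.6–5 | 5.1–10 | >10 |
| Amylase | 1.1–1.5 | 1.6–2.0 | 2.1–5.0 | >5.1 |
| Bilirubin | 1.1–1.5 | 1.6–2.5 | 2.6–5 | >5 |
| Creatinine | 1.1–1.5 | 1.6–3.0 | 3.1–6 | >6 |

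**Step 1: size of the overlap.** Overlap = smaller upper bound − larger lower bound.

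- Grades 1 and 2, for ALP and for GGT: 2.5 − 1.6 = 0.9.
- Share of the Grade 1 band: 0.9 / (2.5 − 1.25) = 0.9 / 1.25 = 72%.
- Share of the Grade 2 band: 0.9 / (5 − 1.6) = 0.9 / 3.4 = 26%.
- With ratios reported to one decimal, Grade 1 runs from 1.3 to 2.5, which is 13 values. Those from 1.6 to 2.5, 10 of the 13, also meet Grade 2.

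Only values from 1.25 to just below 1.6 × ULN are Grade 1 without ambiguity.

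**Step 2: is this how the whole table works?** No. The same check on the eight other ULN-based rows (AST, ALT, amylase, bilirubin, BUN, creatinine, PT, aPTT) gives zero overlap between Grades 1 and 2 and between Grades 2 and 3. ALP and GGT also have none between Grades 2 and 3.

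**Step 3: is there a tie-break?** Table 2 in Section 5.3.3 covers only events that Appendix 15 does not list, so it cannot settle a listed item. Section 5.3.5.6 asks for the most extreme severity of a persistent event that worsens over time; it does not address a single value that fits two grades. No other section gives a rule such as taking the higher grade.

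**Step 4: which bound is wrong?** Two single-bound corrections remove the overlap, and they send the disputed values in opposite directions.

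- If Grade 2 starts at 2.6, values from 1.6 to 2.5 are Grade 1. This matches AST, ALT and BUN, the other rows that start Grade 1 at 1.25. ALP and GGT agree with them at every bound except this one.
- If Grade 1 ends at 1.5, values from 1.6 to 2.5 are Grade 2. This matches the step from 1.5 to 1.6 in amylase, bilirubin and creatinine.

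The first has the better support within the table. The second cannot be excluded without the source scale.

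**Step 5: how often can it matter?**

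- Under Section 5.3.5.7 a laboratory result is an adverse event only if it is symptomatic, changes study treatment, leads to an intervention or a change in concomitant therapy, or is judged clinically significant.
- If the ALP rise is a sign of a disease, only the diagnosis is recorded. The section's own example is ALP with cholestasis. Cholestasis is not an Appendix 15 item, so Table 2 would grade it.
- Appendices 1 and 2 schedule chemistry after baseline only at Weeks 32 and 72 and at early termination, with unscheduled draws if clinically indicated.
- Section 5.3.1 collects all adverse events until 28 days after the last dose. The last Q8W dose is at Week 64, so Week 72 falls (72 − 64) × 7 = 56 days later, when only certain serious events are still collected. Nominally, then, Week 32 is the one scheduled on-study draw that feeds ordinary grading in a Q8W patient who completes treatment.

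**The case against.** The strongest case against the point is that it hardly matters. Few draws are scheduled, most mild ALP rises will not become adverse events, and those that signal a disease are recorded as the diagnosis. The GGT row does nothing unless GGT is measured outside the protocol. The liver event of special interest (Sections 5.2.3 and 5.3.5.9) depends on ALT or AST with bilirubin or jaundice, not on an ALP grade. All of this stands, and it sets the importance. It does not remove the contradiction.

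The table also has other untidy edges, such as the gap between 49,000 and 50,000 for platelets and between 5.0 and above 5.1 for amylase. Those are narrow gaps between bands. The ALP fault is a wide range with two valid answers. A fault in transcription is unlikely, because two separate rows carry the same bounds and their neighbors are clean.

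A reader might infer more than the documents support, in four ways:

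- **That 2.6 is certainly the intended bound.** The pattern favors it, but other rows pair 1.5 with 1.6, and the source scale is not reproduced.
- **That 72% of mild ALP events will be misgraded.** The figure is a share of the width of a numeric band, not of patients or events. The documents give no distribution of ALP values.
- **That unmasked site staff could tilt the grades.** Section 4.2.2 does leave site staff other than the visual acuity examiner unmasked, but nothing links this to ALP grading or points to a direction.
- **That grades should be derived centrally.** Section 5.3 assigns severity to the investigator. Once the bounds are reconciled, no change of process is needed.

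**Conclusion.** The ALP row is wrong as written. Values from 1.6 to 2.5 × ULN meet two grades, the operative severity rule offers no tie-break, and ALP is measured in this trial. The GGT row has the same defect but is inactive under the planned panel.

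The consequence is minor. It is confined to the recorded grade of isolated ALP elevations that qualify as adverse events in their own right, and the uncertainty is one grade (1 or 2). No efficacy result and no Hy's Law report depends on it.

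This rests on two assumptions: that the printed bounds are those in force, and that no grading instruction outside the protocol settles the overlap. The number of affected events cannot be estimated from the documents and is probably small.

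**What to change.** In Appendix 15, check the Grade 1 upper bound and the Grade 2 lower bound for alkaline phosphatase and GGT against the source scale, and correct whichever is wrong so that the bands do not overlap. If the source confirms the pattern of the AST, ALT and BUN rows, the change is to the Grade 2 lower bound, to 2.6 × ULN. That value should not be adopted on the analogy alone.

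The cost is a minor text correction to two rows, carried in the next amendment under Section 9.6. Sampling, assessments and the analysis methods stay as they are.

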Appendix 15: WHO Toxicity Grading Scale for Determining the Severity of Adverse Events

ITEM	Grade 1 Toxicity	Grade 2 Toxicity	Grado 3 Tovicity	Grade 4 Toxicity
		Graue 2 TOXICITY	Grade 3 Toxicity	Grade 4 TOXICITY
CHEMISTRIES (con				
Hyperglycemia (note if fasting)	116–160 mg/dL	161–250 mg/dL	251–500 mg/dL	>500 mg/dL or ketoacidosis or seizures
Hypocalcemia (corrected for albumin)	8.4–7.8 mg/dL	7.7–7.0 mg/dL	6.9–6.1 mg/dL	<6.1 mg/dL or life- threatening arrhythmia or tetany
Hypercalcemia (corrected for albumin)	10.6–11.5 mg/dL	11.6–12.5 mg/dL	12.6–13.5 mg/dL	> 13.5 mg/dL or life-threatening arrhythmia
Hypomagnesemia	1.4–1.2 mEq/L	1.1–0.9 mEq/L	0.8-0.6 mEq/L	<0.6 mEq/L or life-threatening arrhythmia
Hypophosphatemia	2.0–2.4 mg/dL	1.5–1.9 mg/dL or replacement Rx required	1.0–1.4 mg/dL intensive Rx or hospitalization required	<1.0 mg/dL or life-threatening arrhythmia
Hyperbilirubinemia	1.1–1.5×ULN	1.6-2.5 × ULN	2.6-5×ULN	> 5 × ULN
BUN	1.25-2.5×ULN	2.6-5×ULN	5.1–10×ULN	> 10 × ULN
Creatinine	1.1–1.5 × ULN	1.6-3.0 × ULN	3.1–6×ULN	>6×ULN or required dialysis
URINALYSIS				
Proteinuria	1+ or < 0.3% or < 3 g/L or 200 mg–1 g loss/day	2–3+ or 0.3%–1.0% or 3–10 g/L or 1–2 g loss/day	4+ or > 1.0% or > 10 g/L or 2–3.5 g loss/day	nephrotic syndrome or > 3.5 g loss/day
Hematuria	Microscopic only	Gross, no clots	Gross+clots	Obstructive or required transfusion
CARDIAC DYSFUNC	CTION			
Cardiac Rhythm		Asymptomatic, transient signs, no Rx required	Recurrent/persistent, no Rx required	Requires treatment
Hypertension	Transient increase, > 20 mm, no Rx	Recurrent, chronic, > 20 mm, Rx required	Requires acute Rx, no hospitalization	Requires hospitalization
Hypotension	Transient orthostatic hypotension, no Rx	Symptoms correctable with oral fluids, Rx	Requires IV fluids, no hospitalization required	Requires hospitalization
Pericarditis	Minimal effusion	Mild/moderate asymptomatic effusion, no Rx	Symptomatic effusion, pain, ECG changes	Tamponade, pericardiocentesis, or surgery required

Appendix 15: WHO Toxicity Grading Scale for Determining the Severity of Adverse Events

ITEM	Grade 1 Toxicity	Grade 2 Toxicity	Grade 3 Toxicity	Grade 4 Toxicity
CARDIAC DYSFUNG	CARDIAC DYSFUNCTION (cont.)			
Hemorrhage, Blood Loss	Microscopic/occult	Mild, no transfusion	Gross blood loss, 1–2 units transfused	Massive blood loss, > 3 units transfused
RESPIRATORY				
Cough	Transient, no Rx	Treatment associated cough, local Rx	Uncontrolled	
Bronchospasm, Acute	Transient, no Rx <80%–70% FEV 1 (or peak flow)	Requires Rx, normalizes with bronchodilator, FEV 1 50%–70% (or peak Flow)	No normalization with bronchodilator, FEV 1 25%–50% (or peak flow retractions)	Cyanosis: FEV 1 <25% (or peak flow) or intubated
GASTROINTESTINA	AL.			
Stomatitis	Mild discomfort, no limits on activity	Some limits on eating/drinking	Eating/talking very limited	Requires IV fluids
Nausea	Mild discomfort, maintains reasonable intake	Moderate discomfort, intake decreased significantly, some activity limited	Severe discomfort, no significant intake, activities limited	Minimal fluid intake
Vomiting	Transient emesis	Occasional/moderate vomiting	Orthostatic hypotension or IV fluids required	Hypotensive shock or hospitalization required for IV fluid therapy
Constipation	Mild	Moderate	Severe	Distensions w/vomiting
Diarrhea	Transient, 3–4 loose stools/day	5–7 loose stools/day	Orthostatic hypotension or >7 loose stools/day or IV fluids required	Hypotensive shock or hospitalization for IV fluid therapy required
NEURO & NEUROM	USCULAR			
Neuro-cerebellar	Slight incoordination, dysdiadochokinesis	Intention tremor, dysmetria, slurred speech, nystagmus	Locomotor ataxia	Incapacitated
Mood	Mild anxiety or depression	Moderate anxiety or depression and therapy required	Severe anxiety or depression or mania, needs assistance	Acute psychosis, incapacitated, requires hospitalization
Neuro Control	Mild difficulty concentrating, no Rx, mild confusion/agitation, ADLs unaffected	Moderate confusion/agitation, some limitation of ADLs, minimal Rx	Severe confusion/agitation, needs assistance for ADLs, therapy required	Toxic psychosis, requires hospitalization

Appendix 15: WHO Toxicity Grading Scale for Determining the Severity of Adverse Events

ITEM	Grade 1 Toxicity	Grade 2 Toxicity	Grade 3 Toxicity	Grade 4 Toxicity	
NEURO & NEURO	NEURO & NEUROMUSCULAR (cont.)				
Muscle Strength	Subjective weakness, no objective symptoms/signs	Mild objective signs/symptoms, no decrease in function	Objective weakness, function limited	Paralysis	
OTHER PARAMET	ERS				
Fever: Oral, >12 hours	37.7°C–38.5°C or 100.0°F–101.5°F	38.6°C-39.5°C or 101.6°F-102.9°F	39.6°C–40.5°C or 103°F–105°F	>40.5 °C or >105 °F	
Headache	Mild, no Rx therapy	Transient, moderate, Rx required	Severe, responds to initial narcotic therapy	Intractable, required repeated narcotic therapy	
Fatigue	No decrease in ADLs	Normal activity decreased 25%–50%	Normal activity decreased > 50%, cannot work	Unable to care for self	
Allergic Reaction	Pruritus without rash	Localized urticaria	Generalized urticaria, angioedema	Anaphylaxis	
Local Reaction	Tenderness or erythema	Induration < 10 cm or phlebitis or inflammation	Induration > 10 cm or ulceration	Necrosis	
Mucocutaneous	Erythema, pruritus	Diffuse, maculopapular rash, dry desquamation	Vesiculation, moist desquamation, or ulceration	Exfoliative dermatitis, mucous membrane involvement or erythema, multiforme or suspected Stevens-Johnson or necrosis requiring surgery	

ADLs=activities of daily living;  $FEV_1$ =forced expiratory volume in 1 second; GGT=gamma-glutamyl transferase; LLN=lower limit of normal; Rx=prescription; ULN=upper limit of normal

